7.13. Treatment Exposure

Exposure to platelet transfusions will be conducted on the mITT set and the SS by reason for transfusion.

One or multiple study platelet transfusions can occur anytime from Study Day 0 to Study Day 27 per subject. If a subject received a platelet unit within four (4) hours of completion of transfusion of the preceding platelet unit, these transfusions will be considered part of a single platelet transfusion episode in analyses.

Additional blood products transfused will be analyzed based on the SS. The number of blood products transfused (other than PTLs), type of blood product transfused, and for RBC transfusions, whether the RBCs were leukocyte-reduced, will be summarized.

7.14. On- Off-Protocol Transfusions

On- and Off-Protocol Transfusion definitions are as follows:

Off-Protocol Transfusion: any kind of PLT transfusion, other than those to which the subject was randomized (MIR PLTs or REF PLTs), regardless of the reason for the transfusion. For subjects

randomized to MIR treatment (MIRASOL), ISBT codes defined by the sponsor as 'Control Allowed' or 'Control NOT Allowed' meet this criterion. For subjects randomized to CONTROL, ISBT codes defined by the sponsor as 'MIRASOL' or 'MIRASOL Not Used' meet this criterion.

On-Protocol Transfusion: non-MIR or MIR treated platelet product transfused according to randomization assignment. For subjects randomized to MIR treatment (MIRASOL), ISBT codes defined by the sponsor as 'MIRASOL' or 'MIRASOL Not Used' meet this criterion. For subjects randomized to CONTROL, ISBT codes defined by the sponsor as 'Control Allowed' or 'Control NOT Allowed' meet this criterion.

On- and off-protocol platelet transfusions will be reported on the SS and summarized by treatment group and reason for transfusion, i.e. prophylactic, therapeutic (bleeding event), and other. The total number of platelet transfusions and the number of transfusions on- and off-protocol will be reported. The mean, median, minimum and maximum number of transfusions per subject will be reported. The number and percent of subjects with at least 1 on-protocol transfusion will be reported along with the median, minimum, and maximum duration of the transfusion period in days. The number and percent of subjects who had at least 75% of transfusions on-protocol (part of the PPS definition) will also be reported.

Each subject's transfusion will be listed along with on- or off-protocol and non-compliance status described in Section 7.12.

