7.5.3. Safety Set

The SS is defined as containing all subjects who have been randomized and undergo at least one (1) PLT transfusion post-randomization, independent of the outcome or successful completion of the procedure. Subjects will be analyzed according to the majority treatment (transfusion type: MIRASOL or CONTROL) received. If there is a tie, i.e. no majority treatment exists, then the subject will be classified into the treatment group to which they were randomized.

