7.5.4. Per Protocol Set

The Per Protocol Set (PPS) is defined as containing all randomized subjects who undergo at least 75% of post-randomization PLT transfusions as per the protocol treatment allocation and have not experienced any major protocol deviations (as described in Section 7.12). For instance, if a subject is randomized to

the MIRASOL arm and has 4 transfusions, 3 of those transfusions must contain MIR-treated Aph PLTs if the subject is to be included in the PPS. Similarly, if the subject had 3 transfusions, all 3 transfusions must contain MIR-treated Aph PLTs if the subject is to be included in the PPS. Subjects eligible for the PPS will be analyzed according to the treatment group to which they were assigned at randomization.

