## 7.14. On- Off-Protocol Transfusions

On- and Off-Protocol Transfusion definitions are as follows:

Off-Protocol Transfusion: any kind of PLT transfusion, other than those to which the subject was randomized (MIR PLTs or REF PLTs), regardless of the reason for the transfusion. For subjects

randomized to MIR treatment (MIRASOL), ISBT codes defined by the sponsor as 'Control Allowed' or 'Control NOT Allowed' meet this criterion. For subjects randomized to CONTROL, ISBT codes defined by the sponsor as 'MIRASOL' or 'MIRASOL Not Used' meet this criterion.

On-Protocol Transfusion: non-MIR or MIR treated platelet product transfused according to randomization assignment. For subjects randomized to MIR treatment (MIRASOL), ISBT codes defined by the sponsor as 'MIRASOL' or 'MIRASOL Not Used' meet this criterion. For subjects randomized to CONTROL, ISBT codes defined by the sponsor as 'Control Allowed' or 'Control NOT Allowed' meet this criterion.

On- and off-protocol platelet transfusions will be reported on the SS and summarized by treatment group and reason for transfusion, i.e. prophylactic, therapeutic (bleeding event), and other. The total number of platelet transfusions and the number of transfusions on- and off-protocol will be reported. The mean, median, minimum and maximum number of transfusions per subject will be reported. The number and percent of subjects with at least 1 on-protocol transfusion will be reported along with the median, minimum, and maximum duration of the transfusion period in days. The number and percent of subjects who had at least 75% of transfusions on-protocol (part of the PPS definition) will also be reported.

Each subject's transfusion will be listed along with on- or off-protocol and non-compliance status described in Section 7.12.

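### The on-/off-protocol transfusion table is planned on the as-treated Safety Set although its labels follow the randomized arm, so subjects who mostly switched product are counted in the other arm's column

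*Protocol*

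**What the plan says.** The Protocol and SAP files carry the same wording on this point.

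- **Label (7.14).** Off-protocol is "any kind of PLT transfusion, other than those to which the subject was randomized (MIR PLTs or REF PLTs"). On-protocol is likewise judged against the randomization assignment.
- **Set for the table (7.14).** "On- and off-protocol platelet transfusions will be reported on the SS and summarized by treatment group and reason for transfusion". The same paragraph adds a row for subjects with at least one on-protocol transfusion, and then: "The number and percent of subjects who had at least 75% of transfusions on-protocol (part of the PPS definition) will also be reported".
- **Columns of that set (7.5.3).** "Subjects will be analyzed according to the majority treatment (transfusion type: MIRASOL or CONTROL) received". On a tie, "then the subject will be classified into the treatment group to which they were randomized".
- **Other sets.** Both the mITT set (7.5.2) and the Per Protocol Set keep the randomized arm. For the latter: "Subjects eligible for the PPS will be analyzed according to the treatment group to which they were assigned at randomization".
- **Permitted product (7.12).** For a MIRASOL subject, a unit coded 'Control Allowed' is compliant, although 7.14 makes it off-protocol. For a CONTROL subject, any MIRASOL-coded unit is non-compliant.
- **Exposure (7.13).** "Exposure to platelet transfusions will be conducted on the mITT set and the SS by reason for transfusion". No on-/off-protocol split is stated.

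**The concern.** The row label follows randomization and the column follows product received. When a subject receives mostly the other product, the two disagree: the subject leaves the arm whose adherence is being described, and the switches are booked as departures in the other arm.

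In a non-inferiority trial, use of conventional product in the MIRASOL arm can pull the arms together, so a reader needs its amount by randomized arm. The plan expects switching, since 8.1.1 devotes a full procedure to off-protocol intervals. Because 7.12 permits it in one direction only, the likely error flatters MIRASOL adherence.

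No other planned summary gives the count by randomized arm. The 7.13 exposure table has no such split. The transfusion listing in 7.14 is not a summary. The non-compliance summary in 7.12 leaves out 'Control Allowed' units given to MIRASOL subjects. The primary-results display in 8.1.3 shows average days, not transfusions.

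**Working it through.** **What follows from the rules alone**, taking product type in 7.5.3 to be classed as in 7.14:

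1. A subject changes column only with more than 50% off-protocol transfusions, because ties stay put. No MIRASOL-randomized subject left in the MIRASOL column can exceed 50%.
2. A MIRASOL-randomized subject with no on-protocol transfusion always moves. Apart from any CONTROL-randomized subject moved in, the MIRASOL row for at least one on-protocol transfusion is therefore 100% by construction.
3. A subject with at least 75% on-protocol never moves, and a subject who moves never has 75%. The numerators of the 75% row are unchanged. Only the denominators shift away from the randomized arms.

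**Size.** The plan states no switching rate, so there is no figure to reproduce. The inputs are:

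- From 6.3.3: 558 mITT subjects at 1:1, that is 279 per arm.
- Assumed: a share s of MIRASOL subjects is mostly switched, with off-protocol share qs = 80%; other MIRASOL subjects have qr = 5% (or 10%); CONTROL has c = 1%; no CONTROL subject is mostly switched; transfusions per subject are equal.

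By randomized arm: MIRASOL = s·qs + (1 − s)·qr; CONTROL = c.

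In the Safety Set columns: MIRASOL = qr; CONTROL = (c + s·qs)/(1 + s).

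At s = 10% and qr = 5%:

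- By randomized arm: 0.10 × 0.80 + 0.90 × 0.05 = 12.5%, vs 1.0%.
- Planned table: 5.0%, vs (0.01 + 0.08)/1.10 = 8.2%.
- Column sizes: 0.90 × 279 ≈ 251 and 1.10 × 279 ≈ 307.

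| s (qr = 5%) | Randomized arm, MIRASOL vs CONTROL | Planned table, MIRASOL vs CONTROL |
|---|---|---|
| 0% | 5.0% vs 1.0% | 5.0% vs 1.0% |
| 2% | 6.5% vs 1.0% | 5.0% vs 2.5% |
| 5% | 8.8% vs 1.0% | 5.0% vs 4.8% |
| 10% | 12.5% vs 1.0% | 5.0% vs 8.2% |
| 15% | 16.2% vs 1.0% | 5.0% vs 11.3% |
| 30% | 27.5% vs 1.0% | 5.0% vs 19.2% |

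The order reverses when s > (qr − c)/(qs − qr). That is 0.04/0.75 = 5.3% if qr = 5%, and 0.09/0.70 = 12.9% if qr = 10%.

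**Check by simulation** (279 per arm, 1 + Poisson(5) transfusions each, beta-distributed off-protocol probability in MIRASOL with mean 10%, CONTROL 1%, 400 replicates):

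- Strongly clustered switching (beta concentration 1): the planned table shows 4.3% vs 6.5% and reverses in 96% of runs. The 75% row goes from 86.1% vs 99.6% to 93.2% vs 92.6%. This matches point 3: 7.6% of MIRASOL subjects move, and 86.1/0.924 = 93.2 while 99.6/1.076 = 92.6.
- Diffuse switching (concentration 5): 8.2% vs 2.9%. MIRASOL is understated, but no run reverses.

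**Two variations.** With identical switching in both arms (10% mostly switched, 5% in the rest), both tables read 12.5% vs 12.5%. If the label were instead re-derived from the Safety Set column, the s = 10% case would read 5.0% vs (0.01 + 0.10 × 0.20)/1.10 = 2.7%, which still understates MIRASOL.

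**The case against.** The strongest reply is that this is a descriptive table. No test, margin or decision rule uses it; the primary test is on the mITT set by randomized arm; and the subject-level listing would let anyone rebuild the count. Dilution is also examined directly: 8.1.2 analyses the primary outcome with off-protocol intervals included and then excluded, and 8.1.4 repeats it on the Per Protocol Set. All of this stands and limits the consequence. It does not make the planned table right.

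It could also be said that the default display by study arm in 7.9 already implies the randomized arm. But 7.9 yields where something else is specified, and 7.5.3 specifies majority product for this set.

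A reader might infer more than the documents support:

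- *That the table will reverse the arms.* Reversal needs switching concentrated in a minority of subjects, at a rate the documents do not give.
- *That the table measures how much of the primary analysis is simulated.* Simulation in 8.1.1 covers assessed days in off-protocol intervals, and a day with mixed product counts as on-protocol. Transfusion counts would not give that quantity even if correctly grouped.
- *That the 75% row should equal the Per Protocol Set count.* That set also requires no major deviations, and the row is labelled only as part of its definition. The fault is the denominators.

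**Conclusion.** The point holds: the definition and the analysis set conflict as written. Whenever a subject receives mostly the other product, the planned table places that subject and the associated switches in the wrong column for an adherence summary.

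The direction, with MIRASOL understated and CONTROL overstated, rests on few CONTROL subjects receiving mostly MIRASOL product, which the one-way allowance in 7.12 makes likely. The size rests wholly on assumed rates. It ranges from nothing (no mostly-switched subjects) through understatement without reversal (8.2% vs 2.9%, against 10% vs 1%) to reversal (5.0% vs 8.2%, against 12.5% vs 1.0%). Confidence is high in the mismatch, not in any particular size. The non-inferiority conclusion is not affected. The change should be made because the correct table costs almost nothing and no other planned summary supplies it.

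**What to change.** In 7.14, change the sentence beginning "On- and off-protocol platelet transfusions will be reported on the SS and summarized by treatment group" so that the table is *reported for all randomized subjects with at least one post-randomization PLT transfusion and summarized by randomized treatment group*, keeping the breakdown by reason. Apply the same basis to the rows for at least one, and at least 75%, on-protocol.

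This keeps the subjects of the Safety Set and changes only the columns. Naming the mITT set instead would be less safe. The wording of 7.5.2, and the reference in 6.3.3 to subjects who never receive an on-study transfusion, could be read as dropping those given only off-protocol product. The row for at least one on-protocol transfusion would then again be 100% by construction.

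If an as-treated Safety Set version is also wanted, it should show product received (MIRASOL or conventional units) without the on-/off-protocol label.

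The cost is one sentence and one table rerun, with no new data and no effect on any test.

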7.15. Subject Disposition

Subject disposition will be listed and summarized. The number of subjects screened, number of subjects in the FAS, mITT set, PPS and SS, the subject's final study status, and the number of subjects terminating the study early with reasons for early termination will be summarized for all subjects.

Subjects with Inclusion/Exclusion criteria deviations will be listed by subject.

8. Efficacy Analysis

A single primary efficacy endpoint will be considered and investigated using a NI design. The primary efficacy endpoint is defined as the number of days on which bleeding was assessed and WHO grade 2 or higher bleeding was evident over the treatment period. The maximum number of days with bleeding assessments will be twenty-eight (28) as this is the duration of the treatment period. Bleeding events are defined using criteria according to the WHO Grading Scale for Bleeding. Appendix I contains the WHO Grading Scale for Bleeding annotated with the study's Bleeding Assessment (MIPLATE Annotated eCRFs) variable identifiers (Bx) and answers that correspond to the bleeding status. Subgroup analyses involving the primary efficacy endpoint will also be conducted.

8.1. Primary Endpoint

Bleeding assessments based on the WHO Grading Scale for Bleeding will be conducted at baseline to assess eligibility prior to randomization, as well as daily starting on Day 0 and continuing to the post-transfusion bleeding assessment OR until transfusion independence (the last day of ten [10] consecutive days without a PLT transfusion). Each bleeding assessment will document the WHO Bleeding Scale components observed over the course of the prior calendar day, from 00:00 to 23:59. As such, the analysis of the Primary Endpoint, and Secondary Endpoint #2, will be based on bleeding assessments collected on Day 1 thru Day 28 which represent bleeds which occurred on Days 0-27.

The total number of days with WHO grade 2 or higher bleeding is obtained by counting the total number of calendar days (00:00 to 23:59) on which bleeding was assessed and found to be present. For example, if a subject has WHO grade 2 bleeding on Day 1, grade 2 bleeding on Day 2, and grade 3 bleeding on Day 3, this is considered 3 days of grade 2 or higher bleeding. Hematomas (bruises), petechiae, and purpura

[figure not shown]
(e.g., types of bleeding that occur under the skin) represent unique cases in which they are only counted as additional days of bleeding if they are new or manifest in another anatomical location.

8.1.1. Primary Analysis

The MIRASOL vs CONTROL group will be compared with respect to the number of days of WHO grade 2 or higher bleeding. This will be carried out by fitting a negative binomial regression model with an offset defined as the natural logarithm (\ln) of the number of days that bleeding was assessed in order to account for the fact that subjects may have different numbers of bleeding assessment days. As an example, if a subject had bleeding assessed on only 10 of 28 days, an “offset” of $\ln(10)$ bleeding assessment days is incorporated into the linear predictor of the model. Similarly, if bleeding is assessed on each of the full 28 days of the planned treatment period, an offset of $\ln(28)$ bleeding assessment days is incorporated. Adjustment using this offset will ensure that bleeding *rates* are calculated and compared between treatment groups and that the variable number of days with bleeding assessments across individuals is appropriately dealt with. Subjects who obtain transfusion independence prior to Day 28 will be assumed to have zero bleeding days between the date of transfusion independence and Day 27 and treated as if they had bleeding assessed on each of those days; these days will therefore contribute to the total number of bleeding assessment days used to calculate the offset. Subjects who drop-out of the study before Day 28 for reasons other than transfusion independence will contribute bleeding data for each of the days bleeding was assessed prior to the time of drop-out; bleeding status will not be simulated beyond the time of drop-out since the use of an appropriately computed offset deals with the variable duration of follow-up.

The handling of data following the administration of an off-protocol transfusion requires discussion. Here an off-protocol transfusion is defined as the transfusion of any kind of PLT product that differs from that to which the subject was randomized (i.e. MIRASOL or CONTROL).

The timeline diagram provided below demonstrates the definition of an off-protocol window, which we sometimes refer to as an off-protocol interval of time. Consider an individual who was recruited and received on-protocol transfusions as needed from day 0 to day $n-1$. On Day n they received an off-protocol transfusion and on Day m they received their first subsequent on-protocol transfusion; no off-protocol transfusions were received beyond Day m . In order to avoid attributing bleeding outcomes to the randomized treatment arm when an off-protocol product is delivered we partition the full treatment period as follows. We define the intervals from day 0 to $n-1$ and m to Day 27 as *on-protocol intervals*, and days n to $m-1$ as an *off-protocol interval*. In the figure below bleeds are represented by red lines on Days 1-2 and on Day 26 for illustration.

To mitigate against the effect of the off-protocol transfusions in the primary endpoint analysis, bleeding data will be simulated for the off-protocol windows (e.g. intervals such as $[n, m-1]$ above) using an

individual-specific bleeding rate estimated as follows. If individual i has any off-protocol intervals of time, then an individual-specific bleeding rate will be computed as $r_i^{on} = B_i^{on} / N_i^{on}$ where B_i^{on} is the number of on-protocol days during which this individual experienced, and had documented, at least WHO grade 2 or higher bleeding. N_i^{on} is the number of days on which bleeding was assessed during the on-protocol intervals for this subject. Then a) the number of days bleeding was assessed during the off-protocol interval will be computed (N_i^{off}) and b) the number of these days during which WHO ≥ 2 grade bleeding is present will be simulated (B_s^{off}) based on a right-truncated Poisson distribution using the individualized bleeding rate (r_i^{on}). The right-truncation limit will be the total number of off-protocol days (N_i^{off}) since there cannot be more bleedings days than there are days at risk. Specifically, for each individual, counts will be simulated from a Poisson distribution using $r_i^{on} \times N_i^{off}$ as the mean. A simple rejection sampling technique [1] will be used to sample from the right-truncation distribution whereby all values generated which exceed the right truncation limit will be ignored until one is generated that satisfies the right truncation condition. This value will be labelled B_i^{off} . Then the total $B_i^{on} + B_i^{off}$ will be taken as the number of bleeds for that individual experienced over $N_i^{on} + N_i^{off}$ days of assessments; then $\ln(N_i^{on} + N_i^{off})$ will be used as the offset.

If the bleeding rate estimated based on available data $r_i^{on} = 0$ then there will be no bleeding days simulated for the off-protocol days ($B_i^{off} = 0$) and the offset will still be calculated as $\ln(N_i^{on} + N_i^{off})$. Note that for individuals whose last transfusion is off-protocol, at most 10 days of bleeding data after the last transfusion will be simulated as patients going ten (10) days without a transfusion will have acquired transfusion independence.

On occasions where a subject receives a mix of off-protocol and on-protocol units on the same day, they will be considered in an on-protocol period on that day. Transfusions can last more than one calendar day. The daily on- and off-protocol statuses will be assigned for the day the transfusion(s) starts. For subjects whose last transfusion is off-protocol, bleeding will be simulated until the subject completes the transfusion period or reaches transfusion independence. If the subject achieves transfusion independence prior to completing the transfusion period, the rules for transfusion independence will take over and subjects will be assumed to have zero bleeds and full follow-up from the day of transfusion independence until Day 27 inclusive (i.e. the remainder of the transfusion period).

Unless otherwise stated any subsequent analysis herein referring to the primary endpoint method will include the individualized simulated bleeding data for the off-protocol periods of time. This simulation will be done twice. Once at the IA and once at the final analysis. The set of simulations done for the primary efficacy analysis will be used for all subsequent analyses wherein off-protocol intervals are called to use simulated bleeding data.

8.1.2. Secondary Analyses

First Secondary Analysis: Off-Protocol Intervals Included with No Adjustments

In a secondary analysis of the primary outcome all available bleeding assessment data, whether collected on- or off-protocol, will be used and attributed to the randomized treatment in the spirit of an intention to treat analysis. No imputation will be carried out for bleeding status on days following drop-out as the offset deals with censoring and the resulting variation in the days at risk.

Second Secondary Analysis: Off-Protocol Intervals Excluded

In another secondary analysis of the primary outcome, bleeding data will be excluded during off-protocol intervals and the offset will be computed based on the number of on-protocol days which bleeding was assessed for the negative-binomial model. Subjects who obtain transfusion independence while on-protocol will be assumed to experience no further WHO grade 2 or higher bleeding and treated as if they

had bleeding assessed on each of those days. No bleeding data will be imputed following dropout if it occurs and the offset will accommodate different durations of time at risk.

First Sensitivity Analysis: Imputing Bleeding Status for Missing Data

In the analyses discussed to this point, on-protocol days without bleeding data recorded are not counted in the total number of days at risk. An additional sensitivity analysis will be carried out using a negative binomial model for imputing bleeding status on the on-protocol days when bleeding data is missing [2]. First, off-protocol periods of time will use the simulated bleeding rate simulated for the primary analysis in Section 8.1.1. Then the imputation for missing bleeding assessment days will be carried out by fitting an auxiliary negative binomial imputation model to the available data including these covariates: age, sex, treatment arm, treatment type strata, and pre-treatment platelet count. The imputation model will be run fifty (50) times and PROC MIANALYZE will be used to adjust variance estimates for multiply imputed data.

Second Sensitivity Analysis: Poisson Model with Robust Variance

In addition to fitting a negative binomial model to the data from completed and simulated observations, a Poisson model with robust variance estimation will be fit as a sensitivity analysis to the primary analysis.

